FINAL REPORT

**EFFECT OF LIRAGLUTIDE ON EPICARDIAL FAT
IN SUBJECTS WITH TYPE 2 DIABETES**

INVESTIGATOR-INITIATED STUDY

NCT 2014740

University of Miami Clinical Trial # 20120811

[name] [name]

Professor of Clinical Medicine

Director of University of Miami Hospital Diabetes Service

Division of Endocrinology, Diabetes and Metabolism, Department of Medicine,
University of Miami, Miller School of Medicine, Miami, FL, USA

[contact]

SUMMARY

Background Epicardial adipose tissue (EAT) is a peculiar visceral fat depot with anatomical and functional contiguity to the myocardium and coronary arteries. EAT is a highly inflammatory tissue enriched with genes involved in endothelial function, coagulation, immune signalling, lipid metabolism, potassium transport and apoptosis. EAT is associated with coronary artery disease, diabetes and obesity. EAT is easily measurable and an emerging therapeutic target that responds and modifies to medications targeting the adipose tissue. Liraglutide, an analogue of glucagon-like peptide-1 (GLP-1), is indicated for the treatment of type 2 diabetes mellitus. Liraglutide has recently shown to reduce cardiovascular risk. Nevertheless, whether liraglutide could reduce EAT is unknown.

Aim The primary objective of this interventional study was to evaluate whether liraglutide can cause a significant and rapid reduction of EAT, organ-specific visceral fat and cardiovascular risk factor itself, in overweight/obese type 2 diabetic patients.

Methods To test this hypothesis we performed a 6-month randomized, open-label, controlled study in 100 type 2 diabetic subjects with body mass index (BMI) $\geq 27 \text{ kg/m}^2$ and HemoglobinA1c (HbA1c) $\leq 8\%$ on metformin monotherapy. Individuals were randomized in 2 groups to receive additional liraglutide up to 1.8 mg sc once daily ($n=55$) or to remain on metformin up to 1000 mg twice daily ($n=45$). Ultrasound-measured EAT thickness was measured at baseline, 3 and 6-month follow ups.

Results In the liraglutide group EAT decreased from 9.6 ± 2 to 6.8 ± 1.5 and 6.2 ± 1.5 mm ($p < 0.001$), accounting for a -29% and -36% of reduction at 3 and 6 months, respectively, whereas there was no EAT reduction in the metformin group; BMI and HbA1c improved only in the liraglutide group after 6 months.

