Blood Measurements Fasting blood samples for fasting blood glucose (FBG) and HbA1c were obtained from all individuals according to the study design timetable. Blood parameters were measured according to standard and previously described procedures. Fasting comprehensive metabolic panel and lipid profile were also measured at each visit as standard diabetes care.

Follow up of glucose profile Study patients were advised to monitor their capillary glucose twice daily, fasting in the morning and post-prandially. Glucose profile was tracked weekly by the research coordinator and/or principal investigator who were in contact with study patients throughout MyUHealth e-mail system or by telephone.

STATISTICAL ANALYSIS

Primary outcome of the study was EAT changes on liraglutide combined to metformin vs metformin monotherapy; secondary outcomes were determinants of HbA1c changes during treatment. Assuming a difference of 1 ± 0.5 mm in EAT to be clinically significant and using a significance level of $p<0.05$ and 90% power, the current study sample size was sufficient to detect statistical significant differences in EAT between liraglutide and metformin group. Continuous variables were considered as age-adjusted and sex-adjusted means with their standard deviations (SDs). Patients were randomized consecutively using a computer generated randomization table. Two-sample t test with 95 % CI for difference was performed to evaluate differences between the two groups at baseline. Two-way ANOVA was used to calculate changes (Δ) in EAT and other study variables between baseline, 3 and 6 months in both groups. Relations between study variables were calculated using simple linear regression analysis. Two-tailed $p < 0.05$ indicates statistical significance. Statistical analysis was performed using Minitab 17 Software.

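### Displayed means are called age- and sex-adjusted but no listed test names a covariate, and the primary between-arm EAT change has no planned or reported confidence interval

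*Combined protocol and SAP*

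**What the plan says.** All of the analysis text is in the STATISTICAL ANALYSIS section. The primary outcome is a contrast between arms: "Primary outcome of the study was EAT changes on liraglutide combined to metformin vs metformin monotherapy".

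The section attaches age and sex to the summary statistics only, presenting continuous variables as "age-adjusted and sex-adjusted means with their standard deviations (SDs". It gives no model for that adjustment and does not say whether the SDs are raw or residual.

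Three methods are then listed:

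- Baseline: "Two-sample t test with 95 % CI for difference was performed to evaluate differences between the two groups at baseline".
- Change over time: "Two-way ANOVA was used to calculate changes (Δ) in EAT and other study variables between baseline, 3 and 6 months in both groups".
- Associations: "Relations between study variables were calculated using simple linear regression analysis".

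No covariate is named in any of them, and the baseline comparison is the only place where an interval is mentioned.

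In the SUMMARY, the Results paragraph reports "In the liraglutide group EAT decreased from 9.6 ± 2 to 6.8 ± 1.5 and 6.2 ± 1.5 mm" with p < 0.001 and percentage reductions. For the comparator it says "whereas there was no EAT reduction in the metformin group". It gives no metformin mean or SD, no between-arm difference and no interval.

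**The concern.** Two separate points arise.

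**Display and test.** If the printed means are adjusted for age and sex and the p-values come from tests that are not, the two describe different estimates. The plan does not let a reader rule this out. A reader also cannot tell whether 9.6 ± 2 is a raw mean with a raw SD, an adjusted mean with a raw SD, or an adjusted mean with a residual SD. In every case an SD describes spread between patients. It does not give the precision of an adjusted mean.

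**No interval for the primary effect.** The trial asks how much more EAT changes on liraglutide than on metformin alone. The plan gives an interval for the baseline difference, which under sound randomisation is a chance difference, and none for the treatment effect. The plan treats 1 mm as clinically significant, so a reader needs the between-arm difference and its interval to judge the result against that figure. Neither can be recovered from the report.

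**Working it through.** **1. Which analyses can contain age and sex?**

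| Method listed | Used for | Covariates named | Interval named |
|---|---|---|---|
| Adjusted means with SD | display | age, sex | none |
| Two-sample t test | baseline | none (the method has no place for any) | 95% CI |
| Two-way ANOVA | change in EAT and other variables | none | none |
| Simple linear regression | associations | none (single predictor) | none |

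The t test and the simple regression cannot carry extra covariates. The ANOVA factors are not listed. Group and visit is the natural reading of a two-way analysis over three visits in two groups, but the text does not say so.

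**2. The reported change.** From the SUMMARY means, (6.8 - 9.6)/9.6 = -29.2% (stated -29%). At 6 months, (6.2 - 9.6)/9.6 = -35.4% (stated -36%, within the 34.6-36.3% that rounding of the means allows). These figures reproduce, but they are within-arm changes and not the primary contrast.

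**3. Can the between-arm interval be rebuilt?** No. The documents give neither metformin EAT values nor an SD of change. For illustration only, assume zero metformin change, the same change SD in both arms, and complete data (55 and 45):

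- SD of change = sqrt(2² + 1.5² - 2·r·2·1.5), where r is the assumed baseline-to-6-month correlation.
- Half-width = 1.984 × SD of change × sqrt(1/55 + 1/45).

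| r (assumed) | SD of change | 95% CI around -3.4 mm |
|---|---|---|
| 0 | 2.50 | -4.40 to -2.40 |
| 0.5 | 1.80 | -4.12 to -2.68 |
| 0.9 | 0.92 | -3.77 to -3.03 |

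The half-width runs from 1.00 to 0.37 mm, a 2.7-fold range set entirely by a quantity that is not reported.

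**4. What would adjusting for baseline EAT gain?** The liraglutide SDs of 2 (baseline) and 1.5 (6 months) are from the SUMMARY. The metformin SD of 2 at both visits and r = 0.5-0.7 are assumptions. No gain from age and sex is counted.

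- Change-score variance: liraglutide 6.25 - 6r; metformin 8 - 8r.
- Baseline-adjusted variance: liraglutide 2.25(1 - r²); metformin 4(1 - r²).
- Variance of the between-arm difference = liraglutide/55 + metformin/45.

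| | r = 0.5 | r = 0.7 |
|---|---|---|
| Change score: liraglutide, metformin | 3.25, 4.00 | 2.05, 2.40 |
| Adjusted: liraglutide, metformin | 1.69, 3.00 | 1.15, 2.04 |
| Variance of difference, change score | 0.148 | 0.0906 |
| Variance of difference, adjusted | 0.0973 | 0.0662 |
| SE, change score to adjusted (mm) | 0.385 to 0.312 | 0.301 to 0.257 |
| Reduction in SE | 18.9% | 14.5% |

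These figures let each arm have its own slope on baseline. A single common slope (the sample-size-weighted average of the two) gives 18.6% and 13.7%. Either way the SE is about 14-19% smaller.

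**The case against.** The strongest reply is that much of this rests on silence. The ANOVA factors are not listed, and the sentence on adjusted means could be read as covering the analysed values as well as the printed ones. That stands. The supportable statement is that the means and p-values may come from different models, not that they do.

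Baseline EAT is also not ignored, because the ANOVA spans the baseline visit. Using it as a covariate is an efficiency choice and does not correct a proven error. The ANOVA could have supplied an interval too, so the missing interval is its own omission and does not follow from the SD wording or the adjustment.

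Some stronger readings are tempting but unsupported:

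- *The SDs are raw and do not belong to adjusted means.* The text does not define them. If age and sex explained 10% of the variance (assumed), an SD of 2.0 would become 1.90 as a residual SD, a modest difference.
- *The ± figures are error bars about seven times too wide.* They are labelled as SDs and no plot is shown. The factor is only sqrt(55) = 7.4 or sqrt(45) = 6.7, and it arises only if the label is ignored.
- *Baseline adjustment would cut the SE by 25-28%.* That follows only from using the liraglutide SDs for both arms, and part of the gain reflects that arm's SD falling from 2 to 1.5. If the metformin SD stays at 2, that arm gains only 8-13%.
- *The finding of a benefit is in doubt.* Under the illustrative assumptions above, even r = 0 gives an interval well away from zero.

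Lastly, the document is headed as a final report, so any model chosen now is post hoc. That is correct and must be stated with the result.

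**Conclusion.** The point holds as a gap in specification and reporting. Two facts are established from the text: age and sex are named for the displayed means and in none of the tests, and no 95% CI is planned or reported for the primary between-arm EAT change. The reporting of the metformin arm in words alone means a reader cannot fill the second gap.

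A baseline-adjusted model would also be a better method than the one described, at almost no cost. The gain of about 14-19% in the between-arm SE is measured against an unadjusted change-score comparison, which is not exactly the stated ANOVA. It depends on the assumed correlation of 0.5-0.7, the assumed metformin SD of 2 mm, and complete data; dropout is not stated. No change in the direction of the effect is shown.

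**What to change.** - Tabulate unadjusted mean (SD) and number of patients for both arms at baseline, 3 and 6 months, labelled as description.
- Take the primary result from one stated model: 6-month EAT on arm, baseline EAT, age and sex. Report the adjusted between-arm difference with SE, 95% CI and p-value. Analyse 3-month EAT the same way as a supporting result.
- Label this analysis post hoc, because results are already known.
- If adjusted means are still shown, take them from that same model and give them with an SE or CI.
- Drop the baseline significance tests and their CI. The descriptive table serves that purpose.

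EAT was measured at all three visits, and the age and sex adjustment shows that both are on file. The cost is revised wording and a re-run on data already held, with no new patients or procedures.

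### The between-group EAT outcome is tied only to an unspecified two-way ANOVA; no follow-up contrast, interval or deciding visit is named, and a baseline-adjusted estimate would supply them

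*Combined protocol and SAP*

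**What the plan says.** STATISTICAL ANALYSIS defines a between-group outcome: "Primary outcome of the study was EAT changes on liraglutide combined to metformin vs metformin monotherapy". No visit is attached to it. The SUMMARY (Methods) gives the measurement times: "Ultrasound-measured EAT thickness was measured at baseline, 3 and 6-month follow ups". The section on study criteria and treatment arms confirms that the same patients were re-examined at each follow-up.

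The one method sentence that mentions EAT change is: "Two-way ANOVA was used to calculate changes (Δ) in EAT and other study variables between baseline, 3 and 6 months in both groups".

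The same paragraph does specify a between-group test with an interval, but for baseline: "Two-sample t test with 95 % CI for difference was performed to evaluate differences between the two groups at baseline". Age- and sex-adjusted means are mentioned there too, without being linked to any test.

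The aim in the SUMMARY concerns both size and speed: "The primary objective of this interventional study was to evaluate whether liraglutide can cause a significant and rapid reduction of EAT". The SUMMARY results report the treated arm: "In the liraglutide group EAT decreased from 9.6 ± 2 to 6.8 ± 1.5 and 6.2 ± 1.5 mm", with p < 0.001. They say in words that metformin produced no reduction. They give no metformin EAT value, between-group difference, interval or between-group p-value.

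**The concern.** Three EAT values from one patient are correlated. A two-way ANOVA can treat them as independent or can include a patient term, and it can be run on raw EAT, on changes from baseline or on successive changes. These versions test different things and have different error rates, and the method sentence does not separate them. A reader therefore cannot tell what the two-tailed 5% threshold means for the randomised comparison.

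The larger loss is in estimation. The question is how much more EAT falls on liraglutide than on metformin by 3 and by 6 months. No between-group contrast with a confidence interval is named for either visit. The only comparison that has one is at baseline, where randomisation makes it least needed.

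**Working it through.** **Inputs from the document.** 55 and 45 patients; liraglutide-arm SDs of 2.0, 1.5 and 1.5 mm at baseline, 3 and 6 months; falls of 9.6 − 6.8 = 2.8 mm and 9.6 − 6.2 = 3.4 mm (SUMMARY).

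**Assumptions.** The same SDs in the metformin arm, complete data, and an equal within-patient correlation ρ between any two visits of 0.3, 0.5, 0.7 or 0.8. The documents give no ρ and no metformin SDs.

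**The plan's own figure.** The sample-size sentence, "Assuming a difference of 1 ± 0.5 mm in EAT to be clinically significant", with 90% power, needs 7 per arm by an exact two-sample t calculation if ±0.5 is read as the SD. The trial size is therefore sufficient on those inputs. The sentence identifies no ANOVA term or visit, so it does not settle the analysis. Power is not part of this point.

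**Step 1. Group term on changes from baseline, no patient term.**
- Variance of each change = 4 + 2.25 − 2ρ(2)(1.5) = 6.25 − 6ρ.
- Covariance of the two changes = 4 + 2.25ρ − 3ρ − 3ρ = 4 − 3.75ρ.
- Their correlation is r = (4 − 3.75ρ)/(6.25 − 6ρ). The true variance of the group contrast is (1 + r) times the assumed one.
- Type I error ≈ 2[1 − Φ(1.96/√(1 + r))].

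**Step 2. Successive changes (0–3 and 3–6 months), no patient term.**
- The variances are 6.25 − 6ρ and 4.5 − 4.5ρ. Their sum, which independence would give, is 10.75 − 10.5ρ.
- The two changes add up to the 6-month change, whose true variance is 6.25 − 6ρ. The ratio is q = (6.25 − 6ρ)/(10.75 − 10.5ρ).
- The group term uses q and the group-by-time term uses 2 − q in the same formula.

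| ρ | r | Group, changes from baseline | q | Group, successive | Group-by-time, successive |
|---|---|---|---|---|---|
| 0.3 | 0.646 | 12.7% | 0.586 | 1.0% | 9.9% |
| 0.5 | 0.654 | 12.7% | 0.591 | 1.1% | 9.9% |
| 0.7 | 0.671 | 12.9% | 0.603 | 1.2% | 9.7% |
| 0.8 | 0.690 | 13.2% | 0.617 | 1.3% | 9.6% |

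Simulation (20,000 trials per setting) agrees: about 13%, about 1%, and 9–11%.

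**Step 3. Other versions, by simulation.** Group-by-time on raw EAT without a patient term rejects about 1.7% at ρ = 0.3, falling to near 0% at 0.8. The repeated-measures interaction rejects 5.0–5.6%. A two-sample t test on the change at 3 or 6 months rejects 4.8–5.3%.

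**Step 4. At the reported falls, with a flat metformin arm (assumed).** Each of these tests of overall between-group change rejected in 100% of trials: the group term on either kind of change, group-by-time on raw EAT, the repeated-measures interaction and the change-score t tests. The group-by-time term on changes from baseline asks only whether the effect differs between the two visits. It rejected in about 5–35%.

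**Step 5. Precision of the between-group difference.**
- Half-width = t × SD × √(1/55 + 1/45), with √(1/55 + 1/45) = 0.201 and t ≈ 1.984.
- Change score: SD = √(6.25 − 6ρ). Baseline-adjusted: residual SD = 1.5√(1 − ρ²).
- The result is the same at 3 and 6 months, because both have SD 1.5 and the same ρ. The small extra term for chance baseline imbalance is ignored.

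| ρ | Change SD (mm) | Half-width (mm) | Adjusted SD (mm) | Half-width (mm) | Narrower by |
|---|---|---|---|---|---|
| 0.3 | 2.11 | ±0.84 | 1.43 | ±0.57 | 32% |
| 0.5 | 1.80 | ±0.72 | 1.30 | ±0.52 | 28% |
| 0.7 | 1.43 | ±0.57 | 1.07 | ±0.43 | 25% |
| 0.8 | 1.20 | ±0.48 | 0.90 | ±0.36 | 25% |

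**The case against.** The strongest reply is that the wording fits an ordinary repeated-measures ANOVA, which roughly holds its level, and that the text never says the patient term was omitted. That stands. A reader might infer that the published test ran at 13% or at near 0%. The documents do not support either, so the rates above only illustrate how much the unstated choices matter. Nor does one direction of error apply throughout: without a patient term, group-by-time is conservative on raw EAT but liberal on successive changes.

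It is also fair that group and time can be read as the factors, and that the ANOVA cell means give a point estimate of the difference in change at each visit. What is missing is a named contrast with its interval. A 2-df interaction test does not provide one.

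A change-score t test would be valid too. Baseline adjustment is therefore a gain in precision and not a repair of validity.

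Finally, the missing between-group results are missing from a summary, and no full results section is in the documents. Their absence is weak evidence about what was analysed. A reader might also infer that the finding of benefit is unsafe. Step 4 does not support that.

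**Conclusion.** The point holds as a gap in specification and estimation. The named method does not identify the test of the randomised comparison and supplies no stated between-group EAT difference with a confidence interval at 3 or 6 months. An error in the fitted model is not shown.

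The illustrative type I error without a patient term runs from near 0% to about 13% across the change-related terms. This rests on the liraglutide SDs holding in both arms, complete data and ρ of 0.3–0.8. The direction of the reported effect is not in question. The practical gain is an interval for the randomised difference that is 25–32% narrower than a change-score interval, under the same assumptions.

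**What to change.** Replace the two-way ANOVA for the primary outcome with a between-group analysis that has the patient as the unit and adjusts for baseline EAT. Two forms would serve:

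- ANCOVA on baseline EAT at each follow-up visit; or
- a linear mixed model for the 3- and 6-month values with group, visit, group-by-visit, baseline EAT, baseline-by-visit and an unstructured within-patient covariance.

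Report the adjusted liraglutide-minus-metformin difference with 95% CI at both visits, and name one visit as the main result, for example 6 months. Age and sex may be added as covariates.

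Also state which ANOVA was run: its factors, response, definition of Δ, error term and deciding term. If it was a repeated-measures ANOVA, say so.

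The cost is a re-run on data already collected and some redrafting, with no extra patients or visits. Because the results are known, the re-analysis must be labelled post hoc.

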instructions by a registered nurse. Metformin regimen was continued. Metformin-group was treated with metformin monotherapy for the duration of the study at the dosage from 500 mg twice daily to a maximum of 1000 mg twice daily. Both groups received lifestyle and diabetes education, as part of the standard care. Patients in both groups were advised to continue with their usual dietary habit and physical activity. Once patient eligibility and written consent were obtained, the study participants were scheduled for the baseline clinic visit. Each patient underwent a transthoracic echocardiographic study, full physical examination and a fasting blood drawn for measurement of blood glucose and haemoglobinA1c (HbA1c) and other parameters. Study patients were then scheduled for follow-up visits at 3 and 6 months and the same visit procedures were repeated at each follow-up visit.

Study procedures

Echocardiographic Epicardial Fat Thickness. EAT thickness was measured according to the method first described and validated by Iacobellis et al. Briefly, EAT was identified as the echo-free space between the outer wall of the myocardium and the visceral layer of pericardium. EAT thickness was measured perpendicularly on the free wall of the right ventricle at end-systole in three cardiac cycles. Maximum EAT thickness was measured at the point on the free wall of the right ventricle along the midline of the ultrasound beam, perpendicular to the aortic annulus, used as the anatomical landmark for this view. The average value of three cardiac cycles was calculated and used for analysis. Echocardiograms were done by an experienced operator who was blinded to the patients' data. Intra-observer reproducibility of echocardiographic measurement of EAT was assessed by the intra-class correlation coefficient.

Physical Examination All anthropometric measures were obtained by the study nurse at each visit. Height (in cm) and weight (in kg) were measured, and BMI was automatically calculated as weight in kilograms divided by the square of height in meters (kg/m^2). Blood pressure was measured in the seated position, using an automated cuff and digital readout, and entered by the study nurse into the electronic database. Resting heart rate was also measured

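### The primary EAT comparison makes no adjustment for baseline EAT, although it was measured in every patient; a baseline-adjusted estimate would be unbiased and more precise

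*Combined protocol and SAP*

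**What the plan says.** The Statistical Analysis section defines the main comparison: "Primary outcome of the study was EAT changes on liraglutide combined to metformin vs metformin monotherapy". The only method it gives for that comparison is: "Two-way ANOVA was used to calculate changes (Δ) in EAT and other study variables between baseline, 3 and 6 months in both groups". It does not say whether the test is the group effect, the group-by-time interaction or a contrast at one visit, and it mentions no patient factor or repeated-measures structure.

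The only adjustment named is for age and sex: "Continuous variables were considered as age-adjusted and sex-adjusted means with their standard deviations (SDs". Baseline enters only as a check between the arms: "Two-sample t test with 95 % CI for difference was performed to evaluate differences between the two groups at baseline". This is also the only place where a confidence interval is mentioned.

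A baseline value was available for each patient. The Summary states: "Ultrasound-measured EAT thickness was measured at baseline, 3 and 6-month follow ups". Under Study Criteria and Treatment Arms, the baseline visit is described as "Each patient underwent a transthoracic echocardiographic study, full physical examination and a fasting blood drawn", and for the 3- and 6-month visits "the same visit procedures were repeated at each follow-up visit". The three EAT values therefore come from the same patients and are correlated.

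**The concern.** A change contrast subtracts the whole baseline value, which is the same as fixing the slope of follow-up EAT on baseline EAT at 1. A model with baseline EAT as a covariate estimates that slope. When the true slope is below 1, the change contrast carries extra baseline noise and subtracts too much of any chance baseline gap between the arms. Over-correction does not arise for a group main effect averaged over all three visits, but the text does not say which effect was used.

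The missing patient term is a second gap. If the three visits per patient were treated as independent, the error rate of the test would be wrong, and its direction would depend on which effect was tested.

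At stake is how exactly the size of the effect is known. The between-arm EAT difference is the trial's main estimate, yet the Summary gives liraglutide-arm means and a statement that metformin showed no reduction, without a between-arm difference or interval. The Conclusions nevertheless stress the size of the fall.

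**Working it through.** **Plan's own figure.** There is none for the precision of the between-arm difference. The sample-size sentence ("Assuming a difference of 1 ± 0.5 mm in EAT to be clinically significant") does not say whether 0.5 mm is the SD of EAT or of its change, so it is used below only as one scenario.

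**Inputs from the Summary.** n = 55 (liraglutide) and 45 (metformin). Liraglutide-arm EAT is 9.6 ± 2 mm at baseline and 6.2 ± 1.5 mm at 6 months, a fall of 9.6 − 6.2 = 3.4 mm.

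**Assumed, because not given.** The baseline-to-follow-up correlation r and the metformin-arm SDs.

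**Formulas.** Let s0 and s1 be the baseline and follow-up SDs in an arm.
- Change variance: s0² + s1² − 2·r·s0·s1.
- Adjusted variance: s1² + b²·s0² − 2·b·r·s0·s1, where b is the pooled within-arm slope.
- SE = √(vL/55 + vM/45). The CI half-width uses t(98) = 1.984.

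**Slope in the liraglutide arm.** It equals r·s1/s0, so it cannot exceed 1.5/2 = 0.75. If the printed 2 is rounded to a whole millimetre, the cap lies between 1.5/2.5 = 0.6 and 1.5/1.5 = 1.0.

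**Main case: liraglutide SD 2 to 1.5, metformin SD 2 to 2.** At r = 0.5:
- b = (54·1.5 + 44·2)/(54·4 + 44·4) = 169/392 = 0.431.
- Change: vL = 4 + 2.25 − 3 = 3.25 and vM = 4 + 4 − 4 = 4. SE = √(3.25/55 + 4/45) = 0.385.
- Adjusted: vL = 1.700 and vM = 3.019. SE = √(1.700/55 + 3.019/45) = 0.313.

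| r | b | SE, change | SE, adjusted | Variance cut | Half-width, mm |
|---|---|---|---|---|---|
| 0.5 | 0.431 | 0.385 | 0.313 | 33.8% | 0.76 → 0.62 |
| 0.7 | 0.604 | 0.301 | 0.260 | 25.5% | 0.60 → 0.52 |
| 0.8 | 0.690 | 0.249 | 0.220 | 21.8% | 0.49 → 0.44 |
| 0.9 | 0.776 | 0.182 | 0.164 | 19.4% | 0.36 → 0.33 |

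**Other assumptions.**
- SD 2 at all visits in both arms: the cut is (1 − r)/2, or 25%, 15%, 10% and 5% at r = 0.5, 0.7, 0.8 and 0.9.
- Liraglutide as printed, metformin 1.5 to 2: 24%, 9% and 4% at r = 0.5, 0.8 and 0.9.
- Liraglutide as printed, metformin 2 to 1.5: 48% and 44% at r = 0.5 and 0.8.
- 0.5 mm as the SD of change, with equal SDs s: r = 1 − 0.25/(2s²) = 0.944 (s = 1.5) or 0.969 (s = 2), and the cut is 2.8% or 1.6%. This is at the edge of the printed figures: SDs of 2 and 1.5 allow an SD of change of 0.5 only if r = 1, since 2 − 1.5 = 0.5.

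**Single-trial difference between the two estimates (main case).** It is about (1 − b) times the chance baseline gap, whose SE is 2·√(1/55 + 1/45) = 0.402 mm. At r = 0.5 its SD is 0.569 × 0.402 = 0.229 mm, giving a median absolute difference of 0.15 mm. Simulation of 20,000 trials with a 3.4 mm effect gave a median of 0.15 mm (95th percentile 0.46) at r = 0.5 and 0.08 mm (0.25) at r = 0.8. Both methods averaged −3.40 mm.

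**Effect on the conclusion.** If the metformin change is zero (assumption), 3.4 mm is 3.4/0.385 = 8.8 SE against 3.4/0.313 = 10.9 SE at r = 0.5, and 13.7 against 15.5 SE at r = 0.8.

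**Patient term.** In 20,000 simulated null trials per r (three visits, SD 2, nominal 5%), omitting the term made the group main effect reject 11.8%, 16.5% and 24.3% of the time at r = 0.3, 0.5 and 0.9. The interaction rejected 1.4%, 0.3% and 0%. With the term, both rejected about 5%.

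**The case against.** The strongest reply is that this is a choice between two valid estimators. The stated outcome is EAT change, a change contrast estimates exactly that, and randomisation keeps it unbiased. Failing to use the most efficient method is not an error, and here it would not alter the conclusion. All of that stands, and it limits the weight of the point.

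The size of the gain also rests on unprinted inputs. Changing only the assumed metformin SDs moves the cut at r = 0.8 from 9% to 44%, so the main case is an illustration and bounds nothing. The printed SDs may themselves be age- and sex-adjusted, and the calculation leaves age and sex out of both models. These points stand too. Even so, adjustment was the more precise method in every combination tried.

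On the patient term, a repeated-measures two-way ANOVA is compatible with the text. The highest rejection rates belong to a group main effect that includes baseline, which does not estimate change. For the interaction, which does, omission makes the test conservative. If the changes at 3 and 6 months were the response, the group effect without a patient term would reject about 10–11% of null trials. So no invalid test has been shown, only that validity cannot be judged from the text. A repeated-measures analysis would correct the error term, but its group-by-time contrast would still be unadjusted for baseline.

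Finally, the Summary is short, and its silence does not prove that no between-arm difference was calculated.

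**Conclusion.** The concern holds as a matter of precision and specification. It is not a matter of bias. The text names no baseline EAT covariate for the primary comparison, although the value was collected. The loss of precision under a change contrast is roughly a fifth to a third of the variance in the main case, with a plausible range from 2–3% to nearly half. These figures assume r between 0.5 and 0.9 (about 0.94 to 0.97 in the planning-SD case), the metformin SDs shown, and a 6-month comparison of 55 with 45 patients without dropout. The direction of the result is unlikely to change; the width of its interval, and its dependence on a chance baseline gap, would. The unstated patient term and primary effect are a reporting gap that accompanies the main point. The change is worth making, with medium confidence in the size of the gain.

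**What to change.** State the terms of the two-way ANOVA: which effect and visit form the primary test, and whether a patient term is included. Beside that result, report the between-arm EAT difference with its 95% CI from a model with baseline EAT, age and sex as covariates. This can be ANCOVA at 6 months, or a repeated-measures model of the 3- and 6-month values with a patient term. Use robust standard errors if the residual SDs differ by arm.

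The cost is one re-run on existing data and a few lines of text. The drawback is that the model is chosen after the results are known. It must therefore be labelled a post hoc sensitivity analysis and shown alongside the stated ANOVA, not in its place.
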